5.5 Concomitant Treatment

Concomitant treatment with ongoing trastuzumab (Herceptin®) or other targeted/biologic agents is allowed: treatment with any other type of chemotherapy or hormonal therapy is not allowed. Prior enrollment in any other clinical trial during chemotherapy or radiation therapy in the preoperative (i.e., neoadjuvant) or adjuvant setting is not an exclusion as long as all other eligibility criteria are met, and the planned assessments on this study can be completed as planned.

The enrollment of a participant in another clinical trial that may randomize to a hormonal therapy other than anastrozole or to anastrozole plus another therapeutic agent is not allowed.

Should the participant develop AIMSS and stay on anastrozole, concomitant enrollment on to a clinical trial for treatment of AIMSS is allowed (see Supportive Care)

5.6 Supportive Care

All supportive measures consistent with optimal patient care will be given throughout the study.

In participants who experience AIMSS, concomitant enrollment in other clinical trials evaluating the roles of medications or other interventions in the treatment of AIMSS is allowed. Any co-enrollment and interventions must be clearly documented in the medical record and reported on the electronic CRF.

NOTE: The co-enrollment of participants to a trial looking to PREVENT the development of AIMSS is not allowed.

5.7 **Duration of Therapy**

Patients will receive protocol therapy for 12 months from registration. After the 12-month study period is completed, patients should continue to take anastrozole or other endocrine therapies in accordance with standard practice guidelines if tolerated.

Patient will receive protocol therapy unless:

- 5.7.1 Extraordinary Medical Circumstances: If at any time the constraints of this protocol are detrimental to the patient's health, protocol treatment should be discontinued. In this event submit data through Medidata Rave according to the schedule in the E1Z11 Forms Completion Guidelines.
- 5.7.2 Patient withdraws consent.
- 5.7.3 Patient experiences unacceptable toxicity.
- 5.7.4 Prohibited non-protocol therapies are administered.

5.8 Duration of Follow-up

For this protocol, all patients, including those who discontinue protocol therapy early, will be followed until the month 12 visit, which should take place approximately 1 year (+/- 4 weeks) after the initiation of anastrozole therapy. For this protocol, all patients, including those who discontinue protocol therapy early,

Rev. 11/13

Rev. 11/13

Rev. 11/13

will be followed **for survival and recurrence** for 5 years from the date of registration.

6. Study Measures

6.1 Patient Reported Outcome Measures Used In This Study Will Include The Following:

- 6.1.1 Health Assessment Questionnaire (HAQ)
- Rev. 11/13 6.1.2 FACT -G. FACT-Breast subscale and FACT-Endocrine Subscale
 - 6.1.3 Assessment of Survivor Concerns (ASC) and Rackovitch Risk Perception Scale will be used to assess fear of recurrence and perceived risk of recurrence.
 - 6.1.4 Treatment Burden
- Rev. Add5 6.1.5 PROsetta Stone Comorbidity Form
 - 6.1.6 SOAPP study Comorbidity Bother Item
 - 6.1.7 PROMIS Physical Function 20 Form
 - 6.2 Patient Reported Outcome Measures To Be Used In This Study
 - 6.2.1 HAQ Al arthralgias are not well defined, and the most careful work to date has been done with the Health Assessment Questionnaire (HAQ) (27), a patient reported instrument used by rheumatologists, and in the ELPh trial organized by COBRA. This instrument is designed for patients with more serious and debilitating arthritic conditions, and not as sensitive for patients with milder symptoms. Use of broader screening questions may detect milder disability but show ceiling effects for severe disability. We will follow the symptom assessment scheme of the COBRA study by Henry et al (4). This will allow us to gain experience with a published approach to case finding in a second population of patients, and for both clinical and genomic datasets to be compared with the ELPh study,

Rev. 11/13

- 6.2.2 FACT Breast and ES The FACT-Breast and Endocrine Subscales are tailored for patients with breast cancer and includes specific questions related to endocrine therapy (28, 29). The FACT-G measures overall health-related quality of life and consists of 4 subscales that measure physical, functional, emotional and social well-being. The FACT-B Trial Outcome Index (TOI) combines the Physical well-being (PWB) and functional well-being (FWB) subscales of the FACT-G with the breast cancer subscale (BCS). The FACT B+ES were used in the ATAC trial (30). Normative data for interpreting results from this study will be available from E1Z03 for FACT Breast and ES data.
- 6.2.3 Fear of Recurrence The Assessment of Survivor Concerns (ASC) is a 5-item questionnaire that has 2 subscales worry about cancer recurring (3 items) and worry about general health (2 items). Each of the items has a Likert response. In the initial paper, Cronbach's alpha was 0.93 for the cancer worry subscale and 0.72 for the health worry subscale. The items are worry about future tests, new cancer, recurrence, death, and health. ECOG has used the 5-item Assessment of Survivor Concerns (31) for the TAILORx trial to assess fear of recurrence.

6.2.5

Version Date: April 13, 2023

The Rakovitch Risk Perception Scale asks respondents to describe perception of the likelihood of breast cancer recurring in the breast, of breast cancer recurring elsewhere, of dying from breast cancer, and of dying from other cancers. It has 4 items ⁽³²⁾.

6.2.4 Treatment Burden - While many factors may contribute to treatment burden, the concept of a single item for global burden has been used in European studies by the SAKK group⁽³³⁾.

Rev. Add5

- PROsetta Stone Comorbidity Items Clinical decision-making regarding cancer treatment takes on additional complexity in the presence of comorbidity (36). Currently, no gold standard exists in the measurement of comorbidity in cancer patients (37). Although comorbidity is often measured through provider checklists based on chart review, patient self-report of comorbidity yields similar information and includes chronic conditions that are sometimes overlooked on provider chart review. The Prosetta Stone comorbidity items have been used across several large NIH-sponsored projects (PROMIS, Neuro-QOL, Toolbox) and it has demonstrated good reliability and validity. An additional item to address cigarette smoking will be included on this measure for this study. This item is added in response to the need for better reporting of tobacco use as a potential factor influencing patient outcomes in NCI sponsored clinical trials (38).
- 6.2.6 The SOAPP Study Comorbidity Bother Item Perception about a patient's capacity to tolerate treatment can influence treatment decisions. In the ECOG SOAPP study (E2Z02), a single item was used to assess the degree to which the patient reported being bothered by conditions other than cancer. In the breast cancer cohort of the SOAPP study, 65.9% of patients reported at least a little bit of bother due to comorbidities (39) There was a strong association seen between this self-reported bother due to comorbidity and symptom burden (40) This single item is thus included to better understand the impact of comorbidity in addition to the Prosetta Stone items.
- 6.2.7 PROMIS Physical Function (PF) Short Form 20a - The PROMIS PF 20a consists of 20 items that assess four subdomains of physical function: upper extremity, lower extremity, central, and activity. Responses to the 20 items are summed to create one single score. The PROMIS PF 20 was developed based on items selected from the PROMIS Physical Function 154 item bank. The PROMIS PF 20a contains IRT-based items selected from the PROMIS PF 154 item bank. The "IRT-based" PROMIS PF20 are selected using IRT information content data from over 21,000 subjects to identify the best items and minor qualitative input to ensure that all major areas of Physical Function/Disability were represented in the instrument, with their strongest items. In a study of 451 rheumatoid arthritis patients, the PF20 form was comparable to the HAQ (41). The PF20 form has not been used in patients with AIMSS and will be validated against the HAQ in this study.

Rev. 4/14

NOTE: Please note, Spanish, Korean, Chinese and Japanese versions of the FACT-B form will be available on the ECOG website. Chinese and Spanish version of the HAQ

will be available on the ECOG website. Also, the Spanish version of the PROMIS Physical Function 20-item scale will be posted to the ECOG website.

7. Study Parameters

7.1 Data Collection

Rev. 11/13 Rev. 4/14 Rev.12/14		Baseline ¹	3, 6, 9 and 12 months ^{12,17}	Symptom onset/At diagnosis of AIMSS ^{13,17}	At discontinuation of Anastrozole due to AIMSS ^{12,17}	One month after discontinuation of Anastrozole due to AIMSS ^{14,12,17}	5 Years Post Registration ¹⁶
	Demographics	Х					
	Vital Status	Х					X
	History & Physical Exam, ECOG PS	Х					
	Physical Exam Joints ²	Х	Χ	X	X		
	Routine Blood Tests ³	Х					
	Medication Form ⁴	Х	Χ	X	X	X	
Rev. 4/14	The Stanford Health Assessment Questionnaire (HAQ) and PROMIS Physical Function- Short Form 20a ^{5,6}	X ⁵	Х	Х	×	×	
	Patient-Reported Comorbidity Checklist	Х					
	Provider Completed Comorbidity Form	Х					
Rev. 4/14	FACT-G, FACT-B, and FACT-ES ⁶	Х	Х	Х	Х	Х	
Rev. 4/14	Quality of Life (QOL) Battery including Assessment of Survivor Concerns (ASC), Rakovitch Scale, SOAPP Comorbidity Bother, and SOAP Treatment Burden ⁶	х	Х	Х	X	Х	
1160.4/14	Physician Questionnaire ⁷			Х	Х		
	Recurrence Status ¹⁵	Х	Х	Х	Х		Х
	Pill Calendar ⁸		Χ		Х		
	Biological Sample Submissions ⁹ See Section 10						
	MANDATORY: Blood for Pharmacogenomics (one (1) 10cc yellow top tube) ¹⁰	Х					
	Blood for Banking for Future Research ¹¹ (serum, [one (1) 10cc red top tube]	Х	Х	Х	Х		

E1Z11

Version Date: April 13, 2023

Rev. 12/14 1. Baseline assessments and questionnaires must be completed by patients after consent is signed and prior to the start of study treatment, unless otherwise noted.

- Rev. 11/13
 2. The baseline physical exam is to include physical exam of the joints and should be done within 4 weeks prior to registration. Providers must document presence of any joint abnormalities (ie, deformity, edema, joint tenderness, effusions) and if any decrease in range of motion at each visit. In follow-up, assessment should include any diagnosis of AIMSS and recommendations on anastrozole dosing.
- Rev. 11/13, 3. This refers to blood tests requested by the provider to assess appropriateness to begin hormonal therapy with anastrozole, if the provider would routinely perform any tests. There are no routine blood tests specifically required by the study.
- Rev. 11/13 4. Include a list of interventions being used by the patient for pain or AIMSS on the Medication Form. MD/provider may allow the patient to complete the medication form as long as they check accuracy after patient completes this form.
- Rev. 11/13 5. Patient's baseline pain rating must be completed within 7 days prior to registration. The response will be recorded on the registration checklist.
- Rev. 11/13, 6. If patients want to use the Assessment Center for completing quality of life assessments, the site should complete the registration prior to asking the patient to complete QOL questionnaires so that their case number can be used as an identifier in Assessment Center. The baseline assessment should be done prior to starting treatment with anastrozole. For subsequent visits, if participant is not able to complete the questionnaires online, paper versions should be given for completion in clinic.
- Rev. 11/13 7. Physician impressions and recommendations regarding AIMSS (stop, continue or holiday) should be recorded on the Physician Questionnaire in Medidata Rave. This can be completed by the physician either electronically or on paper, with information transferred to the electronic CRF by the study staff.
- Rev. 11/13 8. Patient pill calendar/diary should be completed by patient and collected by the site at 3, 6, 9 and 12 month visits and at the time patient discontinues taking anastrozole.
- Rev. 11/13 9. Kits are being provided for the collection and shipment of the blood samples. Please refer to Section 10.1.2.1 for instructions.
- Rev. 11/13 10. Blood collection for DNA for pharmacogenomics is mandatory as outlined in Section 10. Blood is strongly encouraged to be collected at baseline [after registration, prior to treatment] but may be collected at any other time point if unable to collect at baseline.
- Rev. 11/13 11. Blood (serum) should be collected at baseline (after registration, prior to treatment), at three (3) months **OR** onset of AIMSS (if prior to three [3] months), and at twelve (12) months **OR** discontinuation of anastrozole due to AIMSS. Submit from patients who answer "**Yes**" to "*I agree to provide additional blood for research*."
- Rev. 11/13 12. PRO assessments and clinic visits should be completed every 3 months until 1 year (-/+ 4 weeks) after the initiation of anastrozole therapy. In the event that anastrozole is discontinued due to AIMSS, two additional PRO assessments will be administered: At the discontinuation of Anastrozole due to AIMSS and 1 month after discontinuation of anastrozole due to AIMSS. All participants will complete PRO assessments up until 12 months, including participants who discontinue anastrozole early for any reason.
- Rev. 11/13, 13. Within two weeks after the patient first reports possible AIMSS, there must be an MD assessment/visit to confirm diagnosis and complete PRO's. If the decision is made to discontinue anastrozole due to AIMSS during the same visit as Symptom onset/At diagnosis of AIMSS only one additional MD assessment/visit and repeat PROs must occur one month after discontinuation. If discontinuation due to AIMSS and one month after discontinuation.
- Rev. 4/14 14. If the decision is made to discontinue anastrozole due to AIMSS prior to 12 months, a one month follow-up visit after discontinuation must be completed.
- Rev. 11/13 15. All patients will be followed for recurrence status and survival status until 5 years post study registration. No specific imaging or other assessments are required.

- Rev. 4/14 16. Follow-up visits should be done yearly until 5 years post registration, starting after the patient has completed the 12 months of patient assessments.
- Rev. 12/14 17. If the Symptom assessment(s), At discontinuation of Anastrozole due to AIMSS or 1 month after discontinuation of Anastrozole due to AIMSS visits are within one month (+ or -) of any of the regularly scheduled visit (3, 6, 9, 12) only one set of PRO's and one clinic visit are required. The Symptom assessment(s), At discontinuation of Anastrozole due to AIMSS and 1 month after discontinuation of Anastrozole due to AIMSS visits must trump the 3,6,9 and 12 month post registration visits.

8. Drug Formulation and Procurement

This information has been prepared by the ECOG Pharmacy and Nursing Committees.

8.1 Drug Name Anastrozole

8.1.1 Other Names

Arimidex®

8.1.2 Classification

Antineoplastic agent

8.1.3 Mode of Action

Aromatase inhibitor

8.1.4 Storage and Stability

Store at 20-25° degrees Celsius in a dry environment.

8.1.5 Dose Specifics

1 mg by mouth daily.

8.1.6 Preparation

Oral tablet. Ready to use commercial preparation.

8.1.7 Route of Administration

Anastrozole is taken orally.

8.1.8 Incompatibilities

Not applicable.

8.1.9 Availability

Commercially available.

8.1.10 Side Effects

Vasodilation, hot flushes (flashes), diarrhea, nausea, vomiting, asthenia, pain (including back pain), arthritis, arthralgia, fractures, increased liver function tests, hypertension, osteoporosis, peripheral edema, lymphedema, pharyngitis, depression, rash, insomnia, headache, increased cough, dyspnea, fatigue

8.1.11 References

AstraZeneca. Arimidex (anastrozole) tablets prescribing information. Wilmington, DE; 2008 Dec.

9. Statistical Considerations

The primary endpoint is defined as discontinuation of treatment following development of AIMSS. A patient will be considered to have developed AIMSS if there is a 20% or greater decline in scores on the HAQ instrument from baseline within one year. At the time of treatment discontinuation, patients and providers will be asked to rank the reasons for treatment discontinuation. If either the patient or the provider lists pain as the first or second-ranked reason and discontinuation is within 3 months of symptom escalation, this will be considered an event. Patients who are lost to follow-up or whose reason for discontinuation is unknown will be considered to be event-free. From previous studies, it is estimated that 40% of patients will develop symptoms, and 25% of patients will discontinue treatment with Als within 1 year due to development of musculoskeletal symptoms.

The enrollment plan is designed to assure adequate enrollment of minority (Asian and African-American) patients. After 600 patients are enrolled from other racial groups, closure of the study to those subgroups will be terminated and accrual will continue among only Asian and African-American patients. When 200 patients are enrolled from the first remaining racial subgroup, closure of accrual to that subgroup will terminate and all remaining patients will be enrolled from the final remaining subgroup. ECOG Minority CCOPs will be strongly encouraged to participate in order to meet targets for minority accrual. While not a separate accrual cohort, ethnicity (Hispanic/non-Hispanic) will also be considered in the analysis plan.

The approach we will use to conduct genetic analysis will be a comprehensive one that employs a range of technologies to examine germline genetic variants in the DNA of women in this study, the goal being to test for simple associations of these variants with Als-induced events. Our GWAS approach builds upon data and techniques from genome wide trials already conducted as well as data from candidate gene studies. We will use a custom - designed series of variants tested using the ABI Biotrove Open Array™ system. This allows robust testing of 100-300 variants with a technology that has high reliability and reproducibility, since it is based on simple Taqman™ technology. The Indiana COBRA site has extensive experience in developing chips which can be used to screen for complex and difficult-to-identify ESR genotypes, CYP SNPs, and the other hypothesized candidate polymorphisms that will be tested for in this trial. The use of a flexible but robust technology like this is important since new variants are being identified all the time.

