CTSU sites should follow procedures outlined in the protocol for Site registration, Patient Enrollment, Adverse Event Reporting, Data Submission (including ancillary studies), and Drug Procurement.

For patient eligibility or treatment-related questions Contact the Study PI of the Coordinating Group.

[figure not shown]
For questions unrelated to patient eligibility, treatment, or data submission contact the CTSU Help Desk by phone or e-mail:

CTSU General Information Line – [name], or [contact]. All calls and correspondence will be triaged to the appropriate CTSU representative.

For detailed information on the regulatory and monitoring procedures for CTSU sites please review the CTSU Regulatory and Monitoring Procedures policy located on the CTSU members' website https://www.ctsu.org

The CTSU Web site is located at https://www.ctsu.org

Schema

Accrual = 1,000 patients

- Anastrozole will be given 1mg, po daily for 12 months.

 AIMSS diagnosis will be determined clinically by oncology MD or Nurse when patient complains of joint symptoms. See Section 5.

 Decision whether to continue anastrozole or to start a treatment for AIMSS will be made by patient & MD discussion. See Section 5.

 Blood collection is mandatory for pharmacogenomics as outlined in Section 10. If unable to collect at baseline, please collect at any other time point.

Cancer Research Group Version Date: April 13, 2023

1. Introduction

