The exemestane and letrozole pharmacogenomics (ELPh) study, conducted by the Consortium on Breast Pharmacogenomics (COBRA), has provided important data not only regarding the prevalence of the symptoms and drug discontinuation but also for PRO by using the Health Assessment Questionnaire (HAQ), a commonly used rheumatology instrument. [name] and [name] of ECOG are co-founders of the COBRA group. In this prospective comparison of exemestane and letrozole, patients were randomly assigned to either letrozole or exemestane and were evaluated at predefined intervals by study team members and referred to a rheumatologist based upon change in HAQ scores and pain ratings on a visual analog scale (VAS). The study showed that the predefined symptomatic criteria based on the HAQ and VAS successfully provided a means of case definition of an otherwise difficult-to-characterize syndrome (4,5). Improvement or worsening of HAQ score was defined as a decrease or increase, respectively, of more than 0.22 based on data provided from the rheumatology literature⁽¹²⁾. However, the sensitivity, specificity, and generalizability of the ELPh clinical criteria for defining AIMSS clearly need to be confirmed in a larger cohort of a diverse patient population and in other clinical settings. Data from the ELPh study for the first 100 patients showed that median time to onset of symptoms was 1.6 months (range 0.4-10 months), and median time to study discontinuation (for those who stopped taking AI) was 6.1 months (range 2.2-13 months) (4).

Anastrozole was not studied in the ELPh trial, representing a gap in knowledge both as it is a widely prescribed AI, and because anastrozole associated musculoskeletal symptoms have not been phenotypically characterized with the HAQ. Furthermore, as the patients studied by the ELPh and NCIC Clinical Trials Group MA.27 (described below) populations are predominantly Caucasian, further studies in minority populations are urgently needed.

Genetic Predictors of AIMSS: Pharmacogenomic predictors may help identify women at risk for AIMSS since genetic variants that are associated with AI pharmacokinetics, with the effects of estrogen deprivation on bone and other phenotypes have already been described. We briefly review recent important findings that emphasize the importance of this concept as well as its feasibility.

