5.1.1 Treatment

Anastrozole 1 mg, oral, daily for 12 months. Treatment should start within three working days after registration. The patient will be given a pill diary and instructed to complete it and bring it with them to their next MD visit.

5.1.2 Patients should be instructed that when they develop joint pain or stiffness that they should call their MD. Patients should be encouraged to stay on the medication until seen in an office visit.

MD or provider should see the patient within 2 weeks of the patient's call to assess for the likelihood of rheumatologic disease (joints are not red, hot, swollen, or deformed), and determines clinically if the patient has AIMSS, and records his/her impression. The patient completes the questionnaires.

Patient discusses with MD whether to continue or discontinue the drug or start a treatment for AIMSS. A holiday (defined as a drug-free interval of 6 weeks or less) is also an option, as is switching to a different AI, tamoxifen, or participating in a treatment study. The MD will record the recommendation.

- 5.1.3 If and when the patient decides to discontinue anastrozole, the patient will be asked to complete questionnaires. If this was part of a holiday plan, the drug will be considered discontinued if the patient refuses to restart the medication (off the medication for more than 6 weeks).
 - 5.1.3.1 When a patient discontinues the medication, she will be asked for the reasons, and asked to rank them. If pain or other symptoms such as stiffness are the first or second reason, then it will be considered a discontinuation because of AIMSS.
 - 5.1.3.2 The MD will check in with the patient 4-6 weeks later to see if symptoms have resolved, and if anastrozole is discontinued. The patient will complete questionnaires again.

Rev. 11/13

5.1.4 If the patient is to continue anastrozole beyond the 12 months on study, a final questionnaire will be completed at the 12 month time point.

NOTE: All notations of MD above refer to medical protocol (ie, MD, NP or PA); an oncology nurse may also make assessments if felt to be qualified by the Principal Investigator.

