We propose to include all 1000 patients in assessment of patient-reported outcomes. Linear mixed effects models will be used to evaluate changes in symptoms over time on these instruments. For purposes of estimating available statistical power, we consider a hypothetical analysis comparing changes in endocrine symptoms from baseline to 3 months between Caucasian and African-American patients. Total score on the FACT-ES (FACT-B plus ES subscale) will be calculated. Psychometric properties of FACT-ES were reported by Fallowfield et al. (29). In that report, mean scores of 61.61 at baseline (standard deviation 6.65) and 57.03 at 12 weeks (standard deviation 9.03) were reported among 32 women (a decline of 4.52 points). Table 3 shows statistical power and differences in change from baseline that will be detectable assuming a two-sided t-test with 5% Type I error, 85% power, baseline standard deviation of 6.65, intrapatient correlations of 0.4 or 0.6, and QOL completion rates of 90% and 75% across the two time points. There will be good power to detect reasonable differences between groups in changes from baseline.

Table 3. Detectable Differences for an Example Patient-Reported Outcomes Analysis (85% Power)

Intra-Patient Correlation	Standard Deviation of Change	Completion Rate	N Caucasian Patients	N African- American Patients	Detectable Difference
0.4	7.285	90%	540	180	1.88
0.6	5.948	90%	540	180	1.54
0.4	7.285	75%	450	150	2.06
0.6	5.948	75%	450	150	1.68

Rev. 11/13

Similar analyses will be done for the FACT-B subscale and for the Trial Outcome Index, consisting of the FACT-B subscale along with the FACT-G Physical Wellbeing and Functional Well-Being subscales.

In E1Z03, the quality of life companion study to MA27, patients who reported being bothered by side effects of treatment were more likely to discontinue treatment. The impact of patient-reported outcomes, both side effects in general and joint pain in particular, on treatment discontinuation will be examined along with the genotype information to assess the relative significance of both.

Patients will be given a choice regarding their preference for submitting QOL instruments in paper form or electronically. If 90% or more of patients choose the electronic system and if the completion rate among those patients is greater than 90%, then the web-based system would be considered for future trials.

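### The primary endpoint's AIMSS rule counts a fall in HAQ, which the protocol itself calls improvement, and Sections 9 and 5.1.3.1 disagree on what an event is

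*Combined protocol and SAP*

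**What the plan says.** The opening paragraph of Section 9 builds the primary endpoint in three steps.

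- Endpoint: "The primary endpoint is defined as discontinuation of treatment following development of AIMSS".
- AIMSS: a "20% or greater decline in scores on the HAQ instrument from baseline within one year".
- Event: "If either the patient or the provider lists pain as the first or second-ranked reason and discontinuation is within 3 months of symptom escalation". This sentence does not mention HAQ.

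Other sections bear on the same quantity.

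- Section 1.1.1, describing the ELPh study, gives the only statement of HAQ direction: "Improvement or worsening of HAQ score was defined as a decrease or increase, respectively, of more than 0.22".
- Section 6.2.1 links that to this trial: "We will follow the symptom assessment scheme of the COBRA study".
- Section 5.1.3.1 asks the patient to rank her reasons for stopping: "If pain or other symptoms such as stiffness are the first or second reason, then it will be considered a discontinuation because of AIMSS".
- The Schema says "AIMSS diagnosis will be determined clinically by oncology MD or Nurse when patient complains of joint symptoms", and Section 5.1.2 likewise has the provider decide clinically.
- Section 9.1 splits patients by whether they stopped because of musculoskeletal symptoms, without giving a rule.

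**The concern.** There are two separate faults.

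**Direction.** Applied literally, the HAQ rule labels women whose scores improve as having AIMSS and leaves out those who worsen. If HAQ is also a required part of the event, women who stop after worsening would generally be coded event-free. The opposite error is narrow: a woman whose HAQ fell would still have to stop, with pain in the top two, within 3 months of escalation. If the Section 9 definition is also used for the Section 9.2 comparison of recurrence-free and overall survival by AIMSS status, that comparison inherits the reversal.

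**Event definition.** Even with the direction corrected, Sections 9 and 5.1.3.1 classify some women differently, and *development of AIMSS* means a HAQ change in one place and a clinical diagnosis in another.

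This variable is the outcome in all ten SNP tests. Section 1.1.1 criticises earlier studies for lacking a clear phenotype and offers a pre-defined one as this study's contribution. With the definition open, it could be chosen after the data are seen.

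**Working it through.** **1. Direction.** Section 1.1.1 sets decrease as improvement and increase as worsening. Section 9 sets a fall of 20% or more as AIMSS. Could *decline* mean loss of function? The sentence speaks of scores, and Section 9.3 uses the word for a numeric fall: FACT-ES means of 61.61 and 57.03 "were reported among 32 women (a decline of 4.52 points". (The printed means differ by 61.61 − 57.03 = 4.58, which does not affect this point.) No section reverses HAQ scoring for this trial. The rule therefore runs opposite to its evident purpose, which Section 9 signals by referring to symptom escalation.

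**2. Event rules side by side.**

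| Element | Section 9 | Section 5.1.3.1 |
|---|---|---|
| Whose ranking | patient or provider | patient |
| Reason in top two | pain | pain or other symptoms such as stiffness |
| Time window | 3 months from symptom escalation (not defined) | none |
| HAQ criterion | apparently required by the first two sentences, absent from the event sentence | none |

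Three women, setting HAQ aside:

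| Case | Section 9 event sentence | Section 5.1.3.1 |
|---|---|---|
| (a) Patient ranks stiffness first; neither she nor the provider has pain in the top two | no event | event |
| (b) Only the provider has pain in the top two, the patient ranks no such symptom there, and she stops within 3 months | event | no event |
| (c) Patient ranks pain first but stops more than 3 months after escalation | no event | event |

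**3. Threshold form.** Section 9 uses a relative 20%; Section 1.1.1 uses an absolute 0.22. They coincide only where 0.20 × baseline = 0.22, that is at a baseline of 0.22 / 0.20 = 1.10. At a baseline of 0 a relative change is undefined. Criterion 3.1.11 admits only pain scores of 0 to 3, so low baselines are plausible.

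**4. What lost events would cost.** The documents give no overlap between the rules, so this is an illustration with assumed losses. Inputs from Section 9.1: N = 1000, one-sided Cochran-Armitage trend test at 0.0025 (z = 2.807), additive log-odds, Hardy-Weinberg equilibrium. I take MAF q = 0.20, a 20% event rate and OR 1.63 from Table 2.

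- Genotype frequencies g: 0.64, 0.32, 0.04.
- Risk: p_i = 1/(1 + exp(−(a + i·ln 1.63))). Setting Σ g_i p_i = 0.20 gives a = −1.604 and p = 0.167, 0.247, 0.348.
- If a share L of true events is coded event-free regardless of genotype, coded risk is (1 − L)p_i and coded events are R = 200(1 − L), with S = 1000 − R.
- d is the mean allele count in coded cases minus that in coded controls; V0 = 2q(1 − q)(1/R + 1/S); V1 = Var(cases)/R + Var(controls)/S.
- Power = Φ((d − 2.807√V0)/√V1).

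Reproduction with L = 0: (0.1676 − 2.807 × 0.0447)/0.0481 = 0.875, so power is 80.9%. The OR giving exactly 80% power is 1.62, against 1.63 in Table 2. In all 24 cells of Table 2, power at the stated OR is 80.5% to 81.9%, so the table is sound.

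| Loss L | Coded events | d | √V0 | √V1 | Power |
|---|---|---|---|---|---|
| 0% | 200 | 0.1676 | 0.0447 | 0.0481 | 81% |
| 25% | 150 | 0.1577 | 0.0501 | 0.0543 | 62% |
| 50% | 100 | 0.1490 | 0.0596 | 0.0650 | 39% |
| 75% | 50 | 0.1411 | 0.0821 | 0.0900 | 16% |

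A different question is how large an OR for the coded outcome itself can be detected with 80% power. That rises from 1.62 at a 20% coded rate to about 1.7 at 15%, 1.86 at 10% and 2.3 at 5%. The two series should not be mixed.

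**The case against.** The harm from the direction error is conditional twice over: the HAQ sentence must be applied literally and as a requirement. The event sentence omits HAQ, and so do the primary objective and Section 9.1. The intent is plain enough that a programmer might catch the slip. This limits the likely harm but leaves the text wrong, because the first two sentences of Section 9 do tie the endpoint to AIMSS and AIMSS to HAQ.

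It can also be said that Section 9 governs, since it alone announces the primary endpoint, while 5.1.3.1 belongs to the treatment plan and may serve only to trigger the extra questionnaires at discontinuation. That is a reasonable inference. But 5.1.3.1 defines a discontinuation because of AIMSS, essentially the quantity in the primary objective (Section 2.1), and no cross-reference sets a hierarchy.

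The objection to the power figures stands in full as a limit on their use. The loss shares are assumed. Literal reversal as a requirement could remove more events than these shares, and in the rule conflict case (b) adds events under Section 9 while (a) and (c) remove them. Section 9 also expects 25% to stop, not 20%; at 25%, power at OR 1.63 with no loss is about 87%.

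**Conclusion.** The concern holds, and it must be fixed before the outcome is derived. The HAQ rule is reversed relative to the protocol's own statement of direction. Independently, Sections 9 and 5.1.3.1 give conflicting event rules for the outcome of all ten SNP tests.

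The first conclusion rests on reading *decline in scores* as a numeric fall, which Section 9.3 supports, and on Section 6.2.1 carrying the ELPh scheme into this trial. The second needs no assumption beyond the text. The number of women misclassified is unknown. N, alpha and Table 2 stand; what is unsettled is which women count as events. The fall in power from 81% to 62%, 39% or 16% shows sensitivity to assumed losses that do not depend on genotype and is not an estimate.

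**What to change.** 1. In Section 9, define the HAQ criterion as an increase (worsening) from baseline within one year. In the same edit, confirm that a relative 20% is intended rather than an absolute change, and state how it is computed at low or zero baselines.
2. Write one primary event definition in Section 9 and refer to it from 5.1.3.1 and 9.1. It should state:
   - whether the HAQ criterion is required in addition to the ranked reason;
   - whether development of AIMSS means the HAQ criterion or the clinical diagnosis;
   - whose ranking counts;
   - whether stiffness and similar symptoms count alongside pain;
   - whether the 3-month window applies, and what dates symptom escalation.
3. Settle this before outcomes are linked to genotype.

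The cost is one paragraph, two cross-references and the derivation code. Section 7.1 lists HAQ at every patient-reported assessment, and patients already rank their reasons. Two checks remain. First, confirm that the case report form captures the provider's ranked reasons: Section 9 calls for them, but the Section 7.1 note on the Physician Questionnaire mentions only impressions and recommendations. Second, Section 9.3 uses HAQ and PROMIS PF20a together until 480 English-speaking patients have enrolled and does not say what follows. If HAQ is required for the endpoint, confirm that it continues for the rest, at most 1000 − 480 = 520.
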